### **Neuroimaging Biomarkers:**

We will perform structural and resting state functional connectivity MRI with a 3T system prior to active study phase and immediately after active study phase (up to 5 days following final iTBS stimulation). The MRI scans will require about 1 hour in the MRI scanner. During the scan, participants will lie on the table in the magnet while the images are acquired. Instructions may be given through an auditory system. Subjects will wear earplugs and may be fitted for a bite bar to help them to keep their head still during the scans; for studies that enroll older adults, a bite bar will not be used so as to accommodate participants with dentures. These procedures have been used previously in younger and older adults alike, and do not cause undue distress in subjects.

At Baseline and 1 week, our MRI scans will include:

- Anatomical (T1) - 5min
- Resting state fMRI - 24 min
- Resting state ASL - 7 min

-Diffusion-weighted imaging (DWI) - DWI acquisition will take approximately 4 min along 90 non-collinear directions with a b-value=2400s/mm^2.

TOTAL scan time: ~40min

Biomarker measures: We will use a canonical hemodynamic response function (HRF) convolved event-related model with temporal and dispersion derivatives to model the blood oxygen level dependent (BOLD) in the context of a generalized linear model. Separate regressors (convolved with the HRF) will be created for stimulus events in each paradigm. Temporal and dispersion derivatives will be treated as regressors of no interest. A region of interest (ROI) analysis will be performed using our established methods, to identify BOLD-dependent signal change in the dorsolateral prefrontal cortex, subgenual cingulate, and default mode network nodes (right, left). Beta values for each ROI will be extracted for each subject for regression analyses.

## 6. STUDY PROCEDURES

### 6.1 Schedule of Evaluations

Assessment	Screening (Day -50 to Day -5)	Baseline (Day 0)	Active Study (Day 1)	Active Study (Day 2)	Active Study (Day 3)	Active Study (Day 4)	Active Study (Day 5)	Follow up: Immediate (Day 8 to Day 10)	Follow up: 1-month (Day 30 to Day 40)
Informed Consent	X								
Medical History/Records	X								
MRI Safety Form	X								
Structured Clinical Interview	X								
Clinician Administered Scales	X	X	X	X	X	X	X	X	X
Self-Rated Scales	X	X	X	X	X	X	X	X	X
Biometric Data		X	X	X	X	X	X	X	X
MRI		X						X	
Neurocognitive Measures		X						X	
Study Treatment			X	X	X	X	X		
Continue Medications	X	X	X	X	X	X	X	X	X
Monitor for Adverse Events			X	X	X	X	X		

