## STUDY SYNOPSIS

Title	A Pilot Study of iTBS in Bipolar I Depression
Source of Funding	Baszucki Brain Research Fund
Study Population	Participants aged 18+ years old with a diagnosis of bipolar I disorder, current episode depressed
Study Design	A multisite, open label pilot study to investigate the efficacy and safety of a novel accelerated intermittent theta-burst stimulation (iTBS) protocol while assessing for changes in neuroimaging biomarkers associated with treatment response
Primary Objectives	To examine the use of accelerated iTBS to treat symptoms of treatment resistant depression in bipolar I disorder and assess changes in neuroimaging biomarkers that may predict treatment response.
Number of Sites	2
Total number of Participants	10 (5 at each site)
Study Duration	1 year

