### **3. STUDY DESIGN**

In order to establish feasibility of study design and approach, we will conduct an open label pilot trial of treatment using accelerated iTBS over the left dorsolateral prefrontal cortex (LDLPC) (up to five days, up to 10x/day) using the MagVenture MagPro X100 rTMS System. Participants will have individualized treatment targets that will be produced from structural and functional MRI scans using the software services of Magnus Medical. We will enroll a total of 10 outpatient participants at two participating NNDC centers, the Johns Hopkins University and University of Texas at Austin. The participants will be diagnosed with bipolar I disorder, currently depressed, as determined by a SCID-5 assessment at screening [Day -5/-14]. Participants will be asked to remain on their psychotropic medications for stabilization throughout the screening, baseline, active study and follow-up phases of the study. During active study, changes in medication dosages may be made based on clinical judgment as outlined below. Participants will be required to have an established psychiatrist in order to facilitate ongoing care after the trial.

The expected overall study duration is one year. Each patient will have up to 9 total visits over the course of one month. One visit for consent and screening. One visit for baseline clinical and self-report assessments, MRI scan, and neurocognitive tests. Five consecutive day visits (or less per symptom remission as outlined above via MADRS </=10) of 10 hours each for treatment. Two visits for follow-up. One immediately (up to 5 days) after last day of treatment for clinical and self-report assessments, MRI scan, and neurocognitive tests. And another visit 1-month post-treatment visit for clinical and self-report assessments. All costs for the clinical assessments, MRI scans and TMS treatment related to the conduct of the study will be covered by the study at no expense to the patient. Participants will receive \$500 compensation upon completion of last follow up appointment. This study will offer participants a choice to receive payment/reimbursement through the JHU Greenphire ClinCard Program. The standard Greenphire information sheet will be used to explain the use of Greenphire to participants.

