### **Follow-up [Day 8-40]:**

Due to COVID-19 or related considerations, we will perform follow-up assessments via a secure audio/video platform in cases where we cannot conduct in-person assessments or per participant preference.

For participants completing treatment prior to the 5-day period, immediate post-treatment evaluation is defined as up to 5 days after the last day of treatment and 1-month post-treatment evaluation is defined as 25-35 days after the last day of treatment.

Participants will have the same clinical and neurocognitive assessments that were completed during the baseline time-period at the immediate post-treatment and 1-month post-treatment mark. In addition, we will also administer the CGI-BP at these 2 time points.

Participants will complete the following self-report assessments at these two follow-up time points as long as they meet responder/remission criteria:

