## 8. INTERVENTION DISCONTINUATION

Participants are free to withdraw from the study at any time for any reason. Study doctors are to discontinue participants from the study if participants:

- Request early discontinuation or withdraw consent.
- Experience a serious or intolerable adverse event that prevents the participant from continuing.
- In the Investigator's opinion, is experiencing a clinically significant deterioration.
- Conduct a protocol violation, including lack of compliance.
- Are "lost to follow-up" as defined as no response from participant after daily attempts to contact over the planned five day treatment course.
- Encounter other conditions (such as administrative issues or pregnancy).

If a participant discontinues from the study at any time at their own request or at the study clinician's discretion, the reason(s) for discontinuation are to be recorded by the study.

Participants are to continue care with their pre-study care team. If participants do not remit but respond ( $>/=50\%$  decrease on the MADRS from baseline) to treatment by the end of the acute, 5-day treatment series, they may be referred to a TMS clinic. If participants are withdrawn from the study for reasons related to the treatment (typically adverse event within 30 days of last treatment), they will be followed until the event(s) have resolved or no further action is required. The study team will communicate with the participants' pre-study care team to coordinate care.

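### No general adverse-event inquiry is scheduled after Day 5, although the synopsis says the study investigates safety

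*Combined protocol and SAP*

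**What the plan says.** The synopsis describes an "open label pilot study to investigate the efficacy and safety of a novel accelerated" stimulation protocol. The sample is small: "We will enroll a total of 10 outpatient participants".

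The Section 6.1 schedule has nine visit columns. The row "Monitor for Adverse Events" carries a mark in the five treatment-day columns only. Screening, baseline, the immediate follow-up (Days 8 to 10) and the 1-month follow-up (Days 30 to 40) are blank in that row.

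Section 6.2 describes what happens at the two follow-up visits. On the clinician side: "Participants will have the same clinical and neurocognitive assessments that were completed during the baseline time-period at the immediate post-treatment and 1-month post-treatment mark". The baseline clinical set is the MADRS, YMRS and CGI-BP. On the self-report side, the list, which includes the C-SSRS, is conditional: "Participants will complete the following self-report assessments at these two follow-up time points as long as they meet responder/remission criteria". Neither list contains an adverse-event question, checklist or form.

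Section 7.1 gives methods for seizure, mania and suicide, and places the C-SSRS at follow-up with no response condition. Section 7.3 requires reporting of all adverse events in the study, and Section 7.4 requires known events to be followed to resolution or transfer of care. Section 8, on participants withdrawn for treatment-related reasons, adds in parentheses "typically adverse event within 30 days of last treatment".

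**The concern.** Reporting rules act on events that someone already knows about. For an event to become known after the last treatment day, a participant has to be asked, has to mention it unprompted, or has to show it on an instrument used for another purpose. The plan schedules the first of these only through Day 5.

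Section 7 names headache, fatigue and stimulation-site discomfort as the most common effects and seizure as a rare serious one. None of the scales repeated at follow-up is described as covering these, nor intercurrent illness or hospital admission. According to the Abstract, the study is meant to lead to a larger multisite trial, so its tolerability record is likely to be relied on. A record with incomplete ascertainment after treatment would look more favourable than the truth.

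**Working it through.** The plan states no figure on this point, so there is none to reproduce. The check is a reading of the schedule against the text, followed by simple arithmetic.

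1. **Is the blank real?** Reading the adverse-event row across the nine columns gives two blanks, five marks, two blanks. In the same table the rows for clinician scales, self-rated scales, biometric data and continued medication carry marks through to the 1-month visit. The blanks are therefore not a sign of a truncated table.

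2. **Does another section fill the gap?**
   - Section 6.2, follow-up: clinical scales, cognitive tests and self-reports; no adverse-event inquiry.
   - Section 7.1: seizure (a physician available during treatment), mania and suicide; no general inquiry.
   - Sections 7.3 and 7.4: reporting and follow-up of events once known; neither elicits new events.
   - Section 8: the 30-day remark concerns participants withdrawn for treatment-related reasons; it sets no collection window for the whole sample.
   - No section states a collection window for adverse events.

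3. **Coverage by visit.** From Day 1 on there are five treatment days and two follow-up visits, 7 in all, of which 5 are marked.

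4. **Coverage by calendar time.** The last visit falls on Day 30 to Day 40. 5/30 = 16.7% and 5/40 = 12.5%. The time without scheduled monitoring is 30 − 5 = 25 to 40 − 5 = 35 days.

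5. **Early finishers.** Section 6.2 sets their 1-month visit 25 to 35 days after the last treatment. If monitoring ends with treatment on day k (an assumption; the plan does not say whether the remaining marked days are attended), coverage is k/(k + 35) to k/(k + 25). For k = 3 that is 3/38 = 7.9% to 3/28 = 10.7%.

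6. **Effect of one missed participant.** With 10 participants, failing to record an event in one who had it lowers the observed proportion by 1/10, that is 10 percentage points. Incomplete ascertainment cannot raise the count, so the direction of any bias is known. Its size is not, because the documents give no rate for events after Day 5.

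7. **The C-SSRS at follow-up.** Section 6.2 makes it conditional on response or remission. Sections 6.3 and 7.1 state it without condition, and the self-rated row in 6.1 is marked at both visits without condition. These cannot all be followed for a non-responder.

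**The case against.** The strongest reply is that the plan does look for the events that matter most in this population. The MADRS, YMRS and CGI-BP are repeated at both follow-up visits for everyone. The MADRS has an item on suicidal thoughts, and YMRS change to the immediate visit is a second primary outcome. Section 7.1 also places the C-SSRS at follow-up. Medication changes are monitored through the whole study and wearable data are collected through follow-up, so some medical events could surface that way. All of this stands. A reader who sees the blank cells might infer that no adverse event is systematically sought after Day 5, and that would be wrong for mania, depressive worsening and suicidal thoughts.

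Three other inferences are tempting and not supported:

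- **That only treatment-day events would be reported.** Section 7.3 has no Day 5 cut-off. The weakness is in elicitation, not in the reporting rule.
- **That non-responders have no suicide-risk check at follow-up.** The MADRS item applies to them, and whether they receive the C-SSRS is contradictory in the text, not settled.
- **That Section 8 sets a 30-day collection period which the schedule then breaches.** It describes follow-up of withdrawn participants.

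It can also be said that safety appears in the synopsis under study design but not in the primary objective, and that Section 9 plans no general adverse-event endpoint or analysis. That is correct, so no planned estimate is shown to be biased. It does not remove the gap, because the adverse-event record will still be the study's evidence on tolerability. Finally, calendar days are a rough measure, since events are elicited at visits and a question at a visit can look back. That favours the fix, because two existing visits could cover the whole gap.

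**Conclusion.** The point holds in a limited form. General and medical adverse events have no scheduled inquiry after Day 5 and no defined collection window, in a study whose synopsis says it investigates safety. Two of the seven visits from Day 1 on, and 25 to 35 of 30 to 40 days, have no scheduled general adverse-event monitoring. Any resulting bias runs toward fewer events; its size cannot be estimated from the documents. This rests on the schedule being followed as printed and on no adverse-event form being used at follow-up that the protocol leaves unmentioned.

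The exact two-sided 95% upper limit for 0 events in 10 participants, 1 − 0.025^(1/10) = 30.8%, should not be read as the size of this problem. It follows from the sample size alone and is the same with or without the change below.

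The C-SSRS matter is a separate contradiction between Section 6.2 and Sections 6.3 and 7.1, not an established absence of assessment. The change is worth making but does not threaten the primary analysis.

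**What to change.** - In Section 6.1, mark "Monitor for Adverse Events" at the immediate and 1-month visits.
- In Section 6.2, add an open adverse-event question at both visits for every participant, whatever their response, covering the time since the last contact.
- State the adverse-event collection window once, and make Sections 6.1, 7.3 and 8 consistent with it.
- Reconcile the responder/remission condition on the follow-up self-reports in Section 6.2, which takes in the C-SSRS, with the unconditional statements in Sections 6.3 and 7.1 and the marks in 6.1. Which rule applies is for the study team to decide.

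The cost is a table edit, a few sentences of text, and a few minutes at two visits that already take place. Sample size and the planned analyses are unaffected.

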## 6.2 Descriptions of Evaluations

### **Screening [Day -5/-50]:**

We will recruit participants from our clinics with a treatment history verifying they meet inclusion/exclusion criteria (see below in Section 5). We will obtain informed consent from the participant and a trained rater will administer a SCID (Structured Clinical Interview for DSM-5) to confirm the diagnosis of bipolar I disorder. Participants will be staged using a modified Maudsley staging method tailored for bipolar depression to determine the severity of treatment resistance. The consenting and clinical screening assessment will be performed in-person, or virtually by secure audio/video platform as works best for the individual and current COVID environment. We will also gather the participants' medical records and review all information to screen for inclusion and exclusion criteria, MRI safety, TMS safety, medical and psychiatric history, a pregnancy test, and current medications.

At the clinical screening assessment, a trained rater will also collect the following assessments:

1. MADRS (Montgomery-Asberg Depression Rating Scale)
2. YMRS (Young Mania Rating Scale)
3. CGI-BP (Clinical Global Impression – Bipolar Disorder)
4. ATHF current and lifetime (Antidepressant Treatment History Form) – ATHF reviews patient antidepressant trials to assess whether patients have had “failed, adequate trials” of various classes of antidepressants.
5. TASS (Transcranial Magnetic Simulation Adult Safety Screen) – a screening form that evaluates prior adverse reaction to TMS and various seizure risk factors and relative contraindications

Participants will also complete the following:

1. AS-18 (Affective Self Rating Scale)
2. PANAS (Positive and Negative Affect Schedule)
3. digiBP (Digital Self-Report Survey of Mood for Bipolar Disorder)
4. MADRS-S (Montgomery-Asberg Depression Rating Scale – Self Rated)
5. C-SSRS (Columbia Suicide Severity Rating Scale)

### **Baseline [Day 0]:**

Baseline visits will be separate from screening visits to confirm stability of symptoms. Participants will have an MRI scan in the morning (see Neuroimaging Biomarker section below for more details).

Baseline clinical measures will include:

1. MADRS
2. YMRS
3. CGI-BP

Baseline self-report measures will include:

1. AS-18
2. PANAS
3. digiBP
4. MADRS-S
5. C-SSRS

Cognitive measures collected using Cambridge Neuropsychological Test Automated Battery (CANTAB) software on a tablet. Neurocognitive Measures will include:

1. Rapid Visual Information Processing (7 min): sensitive tool for assessment of sustained attention
2. Delayed Matching to Sample (7 min): test of attention and recognition.
3. One Touch Stocking of Cambridge (10 min): test of executive function, planning and working memory based upon “Tower of Hanoi”.
4. Stop Signal Task (20 min): test of impulse control and response inhibition.
5. Cambridge Gambling Task (18 min): test of decision making and risk-taking behavior outside a learning context.
6. Emotional Bias Task (Happy-Sad) (4 min): detects perceptual bias in facial emotion perception.
7. Emotional Recognition Task (6 min): measures the ability to identify six basic emotions from facial expressions
8. Multi-Tasking Test (8 min): assesses ability to manage conflicting information and ignore task-irrelevant information

Biometric data will be recorded daily by a wearable device that captures biometric data provided by Magnus Medical. This device will be worn daily from baseline through follow-up. Biometric data measures include:

1. Heart Rate Variability
2. Actigraphy
3. Body Temperature
4. Sweat Chloride

### **Active Study [Day 1-5]:**

TMS sessions will be scheduled in a 5-day sequence, resulting in a total of up to 50 sessions. Prior to each daily treatment series, participants will be asked a short series of

questions assessing medication compliance and substance use, amount and quality of sleep, and any other changes in mood since their last treatment session. We will monitor any medication changes throughout the course of the entire study. Participants will receive up to 10 daily stimulations with active iTBS over the left dorsolateral prefrontal cortex (LDLPFC) (1800 pulses). In the event of depression treatment remission (i.e. MADRS  $\leq 10$ ), treatment emergent mania occurring (defined as an increase of 2 or more points in at least 2 YMRS items), or clinician judgment, LDLPFC treatment will be discontinued and emergent symptoms will be treated by increasing the dose of the participant's anti-manic agent and other pharmacologic measures if necessary as assessed by the onsite clinician.

If participants do not experience a significant increase in manic/hypomanic symptoms ( $\geq 2$  item increase of 2 or more points on the YMRS scale), LDLPFC treatment will continue until MADRS  $\leq 10$  or the end of the 5-day treatment series is reached.

Each session will be separated by a 50-minute break. This separation between stimulation sessions decreases the risk of associated TMS side effects (e.g. irritation from the device, headache). The modified PANAS (items 3, 9, 11, 17, 18, 19) will be administered between every stimulation session to assess for any potential shift towards (hypo)mania. If a significant increase ( $\geq 2$  item increase of 2 or more points) is observed, the YMRS will be administered.

Active study clinical measures collected at beginning and end of each treatment day (unless where noted) will include:

1. YMRS (AM and PM)
2. MADRS (AM, PM, and as clinically indicated)
3. Daily Check-In Form (AM only)

Active study self-report measures collected at end of each treatment day will include:

1. AS-18
2. digiBP
3. MADRS-S

The goal will be to treat participants to remission over the course of 5 days or earlier (when patient achieves remission of symptoms per MADRS  $\leq 10$ ).

### **Follow-up [Day 8-40]:**

Due to COVID-19 or related considerations, we will perform follow-up assessments via a secure audio/video platform in cases where we cannot conduct in-person assessments or per participant preference.

For participants completing treatment prior to the 5-day period, immediate post-treatment evaluation is defined as up to 5 days after the last day of treatment and 1-month post-treatment evaluation is defined as 25-35 days after the last day of treatment.

Participants will have the same clinical and neurocognitive assessments that were completed during the baseline time-period at the immediate post-treatment and 1-month post-treatment mark. In addition, we will also administer the CGI-BP at these 2 time points.

Participants will complete the following self-report assessments at these two follow-up time points as long as they meet responder/remission criteria:

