## 2. BACKGROUND AND RATIONALE

### 2.1 Background on Condition, Disease, or Other Primary Study Focus

Bipolar disorder is a chronic and burdensome illness that affects up to 5% of adults (Merikangas et al., 2011) and is associated with direct and indirect costs of care exceeding \$200 billion annually in the US (Cloutier et al., 2018). Individuals with bipolar disorder spend considerably more time ill with depression than with mania or hypomania symptoms (Miller et al., 2014), such that depression accounts for the majority of the time spent unwell. Bipolar disorder is associated with high rates of morbidity and mortality and is an important contributor to long-term dysfunction due to psychosocial impairment, loss of work productivity and high rates of substance abuse (McIntyre & Calabrese, 2019). Compared to the general population, individuals with bipolar disorder are at greater risk to attempt and complete suicide, especially among individuals experiencing longer periods of depression than mania (Baldessarini et al., 2006). First line treatments for depression are limited in bipolar disorder, and treatment resistance can be up to two times higher when compared to unipolar depression (Tondo et al., 2014).

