- f. Digital Self-Report Survey of Mood for Bipolar Disorder (digiBP): The digiBP is a 6-item digital survey for measuring mood in bipolar disorder. It has three depressive items (depressed mood, fidgeting, fatigue), two manic items (increased energy, rapid speech), and one mixed item (irritability); and recovers two scores (m and d) to measure manic and depressive severity. The digiBP will be filled out at every study encounter: screening, baseline, active study, and follow up.
- g. Montgomery-Asberg Depression Scale-Self Report (MADRS-S): The MADRS-S is the self-report version of the original ten-item clinician rated questionnaire (MADRS). The MADRS-S comprises 9 items rated on a 0-3 point scale which are summed to calculate a total score. This score is then doubled for comparison with the clinician version of the MADRS. The MADRS-S will be filled out at every study encounter: screening, baseline, active study, and follow up.
- h. Columbia Suicide Severity Rating Scale (C-SSRS): The C-SSRS is questionnaire used for suicide assessment. The C-SSRS measures four constructs: the severity of ideation, the intensity of ideation, behavior and lethality. It includes "stem questions," which if endorsed, prompt additional follow-up questions to obtain more information. We will utilize this along with clinical assessment to monitor for participant's suicide risk. The C-SSRS will be filled out at screening, baseline and follow up.

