### **7.1 Methods for Assessing Adverse Events**

Seizure: A physician will be available at all times during treatment to evaluate any participant experiencing a suspected seizure.

Mania: The rTMS parameters used in this study are the least risky because the intervals of stimulation have been shown to be appropriate for theta burst stimulation in the motor system with no adverse outcomes. Moreover, participants' symptoms will be monitored carefully by both members of the research team and clinical staff. The YMRS will be administered daily to check for mania symptoms. If the participant displays an increased YMRS score ( $>/=2$  points) on 2 questions, stimulation will be stopped and patient will be treated for emergent symptoms via increase of their anti-manic agent and other pharmacologic measures as indicated per clinician assessment.

If any of the research team or clinical staff believe that the participant may be showing signs of hypomania/mania, the YMRS will be administered by trained personnel immediately, the researchers will not wait until the daily assessments are conducted. Further, independently, the modified PANAS (items 3, 9, 11, 17, 18, 19) may be administered between every stimulation session to assess for any potential shift towards (hypo)mania. If a significant increase ( $>/=2$  item increase of 2 or more points) is observed, the YMRS will be administered.

**Suicide:** Monitoring participants depressive symptoms will allow the identification of individuals at risk of suicide and therefore the risk of this occurring can be minimized. At screening, baseline, and follow up the C-SSRS will be administered to directly assess suicidal risk. During active study days suicide risk will be screened via the MADRS which has a question to assess suicidal thoughts. Evaluation of the suicidal risk assessments will be made by the research team immediately upon collection of these instruments to determine if any follow-up is needed as described in section 7.2.

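### Section 6.2 gives the follow-up C-SSRS only to responders or remitters, contradicting 6.3 and 7.1; if followed, non-responders have no C-SSRS after baseline

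*Combined protocol and SAP*

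**What the plan says.** The follow-up part of section 6.2 asks participants to complete "self-report assessments at these two follow-up time points as long as they meet responder/remission criteria". The list under that sentence is AS-18, PANAS, digiBP, MADRS-S and C-SSRS.

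Other sections schedule the same instruments without a condition:

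- Section 6.3(h): "The C-SSRS will be filled out at screening, baseline and follow up".
- Section 7.1: "At screening, baseline, and follow up the C-SSRS will be administered to directly assess suicidal risk".
- Section 6.3(g): "The MADRS-S will be filled out at every study encounter: screening, baseline, active study, and follow up". The 6.3 entries for AS-18, PANAS and digiBP also include follow-up.
- Section 6.1: the self-rated scales row is marked at both follow-up visits, with no footnote.

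On treatment days 7.1 relies on a different instrument: "During active study days suicide risk will be screened via the MADRS which has a question to assess suicidal thoughts". The 6.2 list introduced by "Active study self-report measures collected at end of each treatment day will include" contains AS-18, digiBP and MADRS-S, and no C-SSRS.

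**The concern.** For a participant who has not responded, staff at the two sites cannot follow both 6.2 and 7.1. If they follow 6.2, the instrument that 7.1 names as the direct assessment of suicide risk at follow-up is withheld from the participants whose depression improved least. The protocol's background says that "individuals with bipolar disorder are at greater risk to attempt and complete suicide, especially among individuals experiencing longer periods of depression than mania". That sentence compares time spent in each polarity and does not address non-response to a five-day treatment, but it gives no support for assessing unimproved participants less. No rationale for the condition is given.

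Section 6.2 also does not say whether responder status is fixed at the end of treatment or judged again at each visit, so the sites could differ over a participant who responds and then relapses.

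A lesser issue is that any summary of the follow-up self-reports would describe only participants selected on the MADRS. That would tend to flatter the depression self-reports.

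**Working it through.** The plan gives no figure on this point to reproduce. The check is a comparison of text, followed by simple arithmetic on reach.

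**1. When is the C-SSRS given?**

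| Visit | 6.2 | 6.3(h) and 7.1 |
|---|---|---|
| Screening | all | all |
| Baseline (Day 0) | all | all |
| Days 1–5 | not listed | not scheduled (MADRS suicide item instead) |
| Immediate follow-up | responders/remitters only | all |
| 1-month follow-up (Day 30–40) | responders/remitters only | all |

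Under 6.2 a non-responder's last C-SSRS is at Day 0. The interval without one runs from Day 0 to the final visit, that is 30 to 40 days.

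The 6.1 schedule is weaker evidence for the C-SSRS itself. Its self-rated row is not itemised and is also marked on Days 1–5, when no C-SSRS is listed. The C-SSRS conflict rests on 6.3(h) and 7.1; 6.1 supports the broader conflict over self-reports.

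**2. Who passes the condition?**

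Response is a MADRS fall of at least 50% from baseline, and remission is a MADRS of 10 or less (both in 6.2). For baseline score b, the highest follow-up score x that qualifies is the largest x with (b − x)/b ≥ 0.5 or x ≤ 10. Entry requires b ≥ 20, so b/2 ≥ 10 and the response criterion always decides:

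- b = 20: x = 10
- b = 30: x = 15
- b = 40: x = 20
- b = 50: x = 25

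The rule therefore does not track current severity. A fall from 40 to 20 is (40 − 20)/40 = 50%, which qualifies although 20 lies in the moderate band of 6.3(a). A fall from 20 to 11 is (20 − 11)/20 = 45%, with 11 > 10, which does not qualify although 11 lies in the mild band.

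**3. How many participants?**

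Inputs: n = 10 (section 3), two follow-up C-SSRS each, hence 20 scheduled. Let q be the non-response proportion, with status judged once at the end of treatment and participants independent. Then expected non-responders = 10q, expected C-SSRS lost = 20q, and P(at least one) = 1 − (1 − q)^10.

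| q | Source | Non-responders | C-SSRS lost of 20 | P(at least one) |
|---|---|---|---|---|
| 0.1 | 90% response cited in the abstract | 1 | 2 | 1 − 0.9^10 = 0.651 |
| 0.3 | assumption | 3 | 6 | 1 − 0.7^10 = 0.972 |
| 0.5 | assumption | 5 | 10 | 1 − 0.5^10 = 0.999 |

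If status were instead judged at each visit, a participant could lose one of the two, and an initial responder who relapses could lose the second. The loss counts above hold only for the single-judgement reading.

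**The case against.** The strongest reply is that 7.1 is the dedicated safety section, the revision history says the suicidality instruments were clarified there in version 1.7, and staff would naturally let 7.1 govern. On that view 6.2 was simply not brought into line, and the loss is possible rather than established. This stands as a limit on certainty. It does not remove the conflict, because 6.2 is the section that tells staff what to collect at each visit.

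Second, non-responders are not left unwatched. They keep the clinician MADRS with its suicide item at both follow-ups. Escalation under 7.2 is not confined to treatment days, and 7.4 follows adverse events to resolution. Active suicidal risk is excluded at entry and an established psychiatrist is required. All of this stands, and it lowers the severity. But 7.1 describes the MADRS contribution as one question and assigns it to treatment days, whereas 6.3(h) credits the C-SSRS with intensity of ideation, behaviour and lethality as well. The 6.1 row "Monitor for Adverse Events" is marked on Days 1–5 only, so it adds no scheduled check at follow-up.

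Third, the only responder definition that carries a time point (6.2, repeated in section 8) refers to the end of the five-day series. It is written for the referral decision, so it suggests a reading of the follow-up condition without settling it.

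Fourth, no self-report scale is an endpoint in 9.3 or analysed in 9.4, and non-responders still have AS-18, digiBP and MADRS-S from treatment days. The selection problem therefore matters only for descriptive summaries.

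**Conclusion.** The concern holds. Section 6.2 conflicts with 6.3(h) and 7.1 on the follow-up C-SSRS, and with 6.1 and 6.3 on the other four scales. If 6.2 is followed and responder status is judged once, each non-responder loses both follow-up C-SSRS and has none for 30 to 40 days. At the protocol's own cited response rate that means 1 of 10 participants on average, with a 65% chance of at least one. The higher figures rest on assumed non-response of 30% and 50%.

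This is chiefly a safety-monitoring fault. Assessment of suicide risk is weakened, not removed, and the primary analysis of MADRS and YMRS is untouched. It should be fixed, but it does not undermine the trial's main result.

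**What to change.** Delete the responder/remission condition from the follow-up part of 6.2, so that all participants complete the listed scales at both follow-ups, as 6.1, 6.3 and 7.1 already provide. At minimum, take the C-SSRS off the conditional list so that 6.2 agrees with 6.3(h) and 7.1. If a condition is kept for the other scales, state when responder status is judged and label any follow-up summary of them as responders only.

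The cost is one deleted clause. For non-responders it adds the C-SSRS and, if the condition is dropped entirely, 18 + 20 + 6 + 9 = 53 questionnaire items (AS-18, PANAS, digiBP, MADRS-S) per visit, at visits already held for their clinician ratings.
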